Secondary hypothesis: We hypothesize that compared with standard tai ji quan or stretching control, participants in the cognitively enhanced tai ji quan training will retain their intervention gains in the primary outcomes of global cognition and dual-task gait performance at 12 months (post-intervention) follow-up. We also hypothesize that cognitively enhanced tai ji quan training will continue to be superior to either standard tai ji quan or stretching control, at 12-month follow-up, in terms of sustaining the training effect on slowing disease progression to dementia, as indexed by the continued improvement in the mean CDR-SB score from baseline.

Study design

This study is designed as a prospective, assessor-blinded, 3-arm parallel group, randomized clinical trial with a 1:1:1 allocation ratio. The primary co-outcome measures are global cognition function and dual-task walking costs. The target sample size is 315 participants, enrolled from local communities. The goal is to detect, with 80% power, 1.5 points in MoCA between the cognitively enhanced tai ji quan and the standard tai ji quan groups and 3 points between the cognitively enhanced tai ji quan and the stretching control groups at 24 weeks. The study will consist of a 6-month acute intervention phase (designed for addressing the primary aim) followed a 6-month maintenance phase (for addressing the secondary aim).

Outcomes

Table 1 below describes the study's primary, secondary, and tertiary outcomes, source of data, and follow-up schedule.

	Measure	Data source	Follow-up schedule
Primary outcome			
Global cognition	Montreal Cognitive Function	Assessment	4 months, 6 months,
-	measure	conducted by	and 12 months
	(MoCA; score range: 0 to 30)	assessors	
Dual-task walking costs	Difference between single-	Assessment	4 months, 6 months,
	and dual-task gait speed	conducted by	and 12 months
	(expressed in percentage)	assessors	
Secondary outcome			

Cognition and function	Clinical Dementia Rating Sum of Boxes score (range: 0 to 18)	Interviews with participants and informants conducted by assessors	4 months, 6 months, and 12 months
Executive function	Trail Making Test (B) (measured in seconds)	Cognitive assessment conducted by assessors	4 months, 6 months, and 12 months
Attention and memory	Category Fluency (number of animal names recalled)	Cognitive assessment conducted by assessors	4 months, 6 months, and 12 months

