 - Participants' characteristics ascertained at baseline will be compared across intervention groups using independent samples or Wilcoxon rank sum tests, as appropriate, for continuous variables and a chi-square or Fisher's exact tests, as appropriate, for categorical variables. Although no significant differences are expected due to the randomized intervention assignment and the relatively large sample size, any variables found to be significantly different will be noted and accounted for, by controlling for them as covariates in supplements to the main analyses.
- *Time-specific and change scores*. Scores at each follow-up and change in mean scores from baseline at 24 weeks, by intervention group, for all outcome measures will be calculated and presented.
- *Intervention adherence, attrition, and retention*. Class attendance data will be calculated as the average number of scheduled intervention sessions (48 total) attended by participants across intervention groups. Study attrition and retention rates will also be calculated and reported, by intervention group, as the number of participants who completed the 24-week intervention and those who completed all scheduled study follow-up assessments.

Analysis populations

Efficacy analyses. The effect of intervention on the co-primary study outcomes will be evaluated using an intention-to-treat approach in which participants will be analyzed according to randomization assignment. A modified intention-to-treat analysis will be conducted that includes all participants who have undergone randomization and have completed all study follow-up assessments, regardless of their participation adherence status. Finally, a per-protocol analysis will include participants in the intention-to-treat population who have an overall class attendance rate of $\geq 75\%$ (out of the total planned 48 intervention class sessions) of their assigned exercise intervention.¹⁰

Co-primary endpoint analyses

To test the *Primary hypothesis*, we plan to use a generalized linear mixed model with random intercepts and fixed treatment effects for the primary outcomes. Specifically, we will determine the intervention effect through an analysis of a 3 (Group) by 3 (Time) mixed-effects model with repeated measures (follow-up time point) on the second factor (i.e., outcome measures assessed at baseline, 4 months [mid-point], and 6 months [intervention termination]).

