In the presence of a Group by Time interaction effect, follow-up pair-wise comparisons, using independent t tests, will be performed to identify a priori specified between-group differences. Specifically, we will determine the intervention effect of cognitively enhanced tai ji quan for change in MoCA and costs of dual task in gait performance from baseline to 24 weeks by making a comparison between cognitively enhanced tai ji quan and standard tai ji quan and between cognitively enhanced tai ji quan and stretching exercise.

Level of statistical significance and confidence intervals. Our primary outcome analyses will be 2-sided with an adjusted significance level of <0.0125 (0.05 / 4 comparisons) and a 98.75% confidence interval (CI). For each group, both estimated means and their corresponding standard error of estimates at each assessment point will be presented. In presenting between-group differences, mean differences with CIs will be presented. SPSS "MIXED" function will be used in analyzing our primary outcomes.

Secondary and tertiary outcome analyses

A similar analytic approach will also be applied to all secondary and tertiary (continuous) outcome variables described in Table 1. All study outcomes are expected to follow a normal distribution. In the case of deviation from normality, generalized estimating equations will be used to assess the effect of intervention over time. No Bonferroni correction will be made to account for multiple comparisons.

Level of statistical significance and confidence intervals. All tests and CIs will be 2-sided, and statistical significance will be defined as a P value of <0.05. For each group, we will report both estimated means and their corresponding standard error of estimates at each assessment point. In presenting between-group differences at 24 weeks, estimated mean differences with CIs will be presented.

Analyses on examining intervention durability at 48-week follow-up

We will use the same analytic strategy outlined in our primary and secondary outcome analyses, with the exception of CDR-SB (described in detail below), to examine whether the intervention effects will persist 24 weeks after the end of the 24-week supervised interventions (*Secondary hypothesis*).

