With the longitudinal data, we will test the hypothesis that the rate of improvement over time in the mean CDR-SB score, at 24-week post-intervention follow-up, will be greater in the cognitively enhanced tai ji quan group compared with the other two exercise groups. To test this hypothesis, we will use the latent growth curve modeling approach,³⁵ with maximum-likelihood estimation, analyzing the rate of change in the mean CDR-SB score defined by the four measurement time points: baseline, 16 weeks (mid intervention assessment), 24 weeks (end of intervention assessment), and 48 weeks (24 weeks post intervention follow-up).

Accordingly, we will operationalize our basic growth curve model with two latent growth factors: Intercept (defining the initial level of CDR-SB – baseline) and Slope (defining the rate of change over the course of the 48-week study period), with each factor being defined by the four time-specific CDR-SB

measures. A schematic representation of the planned latent growth model to be evaluated for each intervention group is shown in Figure 1. The factor loadings for the Intercept factor will be fixed with a constant value of 1 for all measurement points whereas the loadings for the Slope factor, defining the rate of change over time, will be fixed at 0 for CDR-SB at baseline, 1 for CDR-SB at 16 weeks, 2 for CDR-SB at 24 weeks, and * for CDR-SB at 48 weeks (where * indicating an undefined, free estimate at 48 weeks). All other model parameters to be estimated include latent Intercept mean and its variance, latent Slope mean and its variance, the correlation between Intercept and Slope (covariance), and error variance for each of the four time-specific measurements (shown as E's). The model estimation will include all available data derived from the trial, hence, an intent-to-treat approach.

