The model estimation of change in CDR-SB will involve two steps. First, we will estimate an unconditional latent growth model (i.e., without the group predictor [e.g., cognitively enhanced tai ji quan group vs standard tai ji quan group]). This unconditional growth curve model allows us to examine the overall pattern of change in the CDR-SB score over time. Next, a group predictor (as a binary variable [1=cognitively enhanced tai ji quan group and 2=standard tai ji quan group]) is added to the model parameterization. By regressing the Slope factor on to the predictor of the group variable, this model will examine the pre-specified intervention effect of the cognitively enhanced tai ji quan training, compared with each of other two active groups, individually, on the rate of change in cognitive functioning trajectories. The schematic representation of this second latent growth model with the group, as a predictor, is shown Figure 2 (next page). For reporting purposes, we will present (a) latent slope mean for each group and (b) the regression coefficient relating group and the latent slope (with 95% CI). A negative slope mean for CDR-SB will indicate an improvement in cognitive functioning and, therefore, a lowering of the disease progression, whereas a positive mean slope will indicate deterioration in cognitive functioning.

A statistically significant regression coefficient indicates the difference in the rate of CDR-SB progression. All tests and CIs will be 2-sided, and statistical significance will be defined as a P value of <0.05. The planned statistical analyses on change in CDR-SB will be performed in *Mplus* statistical software version 8.2 (Muthén & Muthén).

[figure not shown]

Figure 1. Latent growth curve model (intercept and slope) of change in CDR-SB over the 48-week study period

Note:

Intercept: defines the CDR-SB score at baseline

[figure not shown]
Slope: defines change or progression in the CDR-SB score from baseline to 48 weeks

*indicating an undefined, freely estimated loading at 48 weeks

Values in the squared box indicates observed value at each measurement time point

E1 through E4 represent measurement error at each measurement time point

Figure 2. Latent growth (intercept and slope) model for examining intervention effect on CDR-SB over the 48-week study period

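### The only 48-week test planned for CDR-SB does not test the week-48 difference

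*Protocol*

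**What the plan says.** The secondary hypothesis, in both the Protocol and the SAP, is that on CDR-SB the enhanced arm "will continue to be superior to either standard tai ji quan or stretching control, at 12-month follow-up". The section on intervention durability at 48-week follow-up treats the other outcomes and CDR-SB differently: "We will use the same analytic strategy outlined in our primary and secondary outcome analyses, with the exception of CDR-SB". CDR-SB instead gets a latent growth model with four visits (baseline, weeks 16, 24 and 48).

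- **Loadings.** Slope loadings are "fixed at 0 for CDR-SB at baseline, 1 for CDR-SB at 16 weeks, 2 for CDR-SB at 24 weeks". The last one is left open: "where * indicating an undefined, free estimate at 48 weeks".
- **Group effect.** "By regressing the Slope factor on to the predictor of the group variable, this model will examine the pre-specified intervention effect". Each comparison with the enhanced arm is fitted separately.
- **Reporting.** The slope mean per arm, and the coefficient of Slope on Group with a 95% CI, tested two-sided at 0.05.
- **Reading.** "A statistically significant regression coefficient indicates the difference in the rate of CDR-SB progression". The note to Figure 1 adds: "Slope: defines change or progression in the CDR-SB score from baseline to 48 weeks".

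Elsewhere, the descriptive section promises "Scores at each follow-up and change in mean scores from baseline at 24 weeks, by intervention group". Between-arm differences with CIs for secondary outcomes are planned at 24 weeks. The Protocol names CDR-SB as the key secondary outcome.

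**The concern.** The hypothesis concerns the state of affairs 24 weeks after training stops, but the tested coefficient is scaled by the visits up to the end of training. Fixing the loadings at 0, 1 and 2 makes one unit of Slope the change per step between on-treatment visits. The free loading then absorbs whatever happens afterwards. Contrary to the note to Figure 1, the coefficient is not a difference in change from baseline to week 48.

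No other planned analysis fills the gap, because CDR-SB is taken out of the strategy used for every other outcome at 48 weeks and its week-48 scores are only described. A significant coefficient would be read as sustained slowing of progression to dementia, even if the benefit had gone by week 48. The primary aim is not affected.

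**Working it through.** **1. Algebra from the plan's own specification.** Code the enhanced arm 1 and the comparator 0. A negative g then favours the enhanced arm, since higher CDR-SB is worse. (The plan codes them 1 and 2, which only flips the sign.) The model mean at visit t is

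E(y_t) = a + λ_t (b + g × Group), with λ = 0, 1, 2, L.

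The modelled arm differences are 0 at baseline, g at week 16, 2g at week 24 and L × g at week 48. Take g = −0.15, so that the week-24 difference is −0.30:

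| L | Week-48 difference |
|---|---|
| −1 | +0.15 (reversed) |
| 0 | 0 (lost) |
| 1 | −0.15 (halved) |
| 2 | −0.30 (kept) |
| 3 | −0.45 (grown) |

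The same g fits every row. This step needs no assumed variance.

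**2. How often a lost effect would be significant.** The plan states no power for this model, so there is no figure to reproduce.

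- From the documents: 267 evaluable participants in three equal arms, 267/3 = 89 per arm; alpha 0.05 two-sided.
- Assumed: SD 1 at every visit; correlations 0–16 .72, 0–24 .70, 0–48 .65, 16–24 .75, 16–48 .68, 24–48 .70; benefit 0.15 SD at week 16 and 0.30 SD at week 24; control worsening linear in weeks.

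The planned model was fitted by maximum likelihood to these population moments, with power from the likelihood-ratio noncentrality. The table gives the probability that g is significant in either direction:

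| Control worsening by week 24 (SD) | Benefit gone at week 48 | Benefit fully kept |
|---|---|---|
| 0 | 88% | 88% |
| 0.05 | 83% | 86% |
| 0.10 | 65% | 75% |
| 0.15 | 37% | 64% |
| 0.20 | 22% | 66% |
| 0.30 | 11% | 71% |

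In the gone column, g has the wrong sign from 0.20 SD. For a 0.5 SD benefit that is gone, the range is 54% to over 99%. With flat controls and a between-person slope variance of 0.05, 0.10 or 0.20 (per 24 weeks squared), the 0.3 SD gone case gives 85%, 67% and 32%.

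**3. Why control drift matters.** One L must serve both arms. Take drift 0.10 with the benefit gone. The control means at weeks 24 and 48 are 0.10 and 0.20: a slope of 0.05 and L = 0.20/0.05 = 4. The enhanced means are −0.20 and 0.20: a slope of −0.10 and L = 0.20/(−0.10) = −2. The fit compromises at L = −2.21 and g = −0.072. Then L × g = +0.159 SD against the enhanced arm, while g favours it and the true week-48 difference is 0.

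**4. Simulation, same assumptions, 150 trials per setting.**

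- Gone, drift 0: 125 significant (83%), all favourable.
- Kept, drift 0: 132 significant (88%).
- Gone, drift 0.10: 88 significant (59%), 86 of them favourable.
- Gone, drift 0.30: 26 significant (17%), 3 favourable and 23 reversed.

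**5. Simulation with other variances** (intercept SD 1.0, error SD 0.5; slope SD 0.2 with g = −0.15, or slope SD 0.4 with g = −0.20; 200 trials each). The coefficient g was significant in 77.5% and 80.5% of trials under complete loss, and in 81.5% and 77.0% when sustained. A t test on change to week 48 rejected in 2.5% and 4.5% under complete loss.

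**6. Direct contrast.** With correlation 0.65, the SD of change is √(2 × (1 − 0.65)) = 0.837. The SE of the arm difference is 0.837 × √(2/89) = 0.125. For a kept 0.30 SD, z = 0.30/0.125 ≈ 2.39, and power is Φ(2.39 − 1.96) ≈ 67%. If the benefit is gone, the rejection rate is 5% by construction (32 of 450 simulated). Control drift cancels.

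**The case against.** - **The hypothesis is partly about a trajectory.** The SAP speaks of a rate of improvement and of continued improvement from baseline, so a slope is not an absurd target. But both statements are placed at the post-intervention follow-up. Nor is g a rate per week: weeks 0, 16 and 24 are proportional to 0, 1 and 1.5, not 0, 1 and 2. That spacing may be deliberate, since cognitive integration is scheduled from week 16, and it is a minor point.
- **Week-48 data do enter the fit.** This is true, and in the second simulation a difference present only at week 48 also made g significant (80% and 65%). The fault is that g is not specific to week 48.
- **The model details are not all visible.** Figure 2 is not shown, and the text does not say outright that both arms share one week-48 loading; that is the natural reading of the second-step model. Letting Group also predict Intercept leaves the gone case at 86%, 66% and 17% for drift 0, 0.10 and 0.30. Separate models per arm would still supply no week-48 test.
- **The percentages rest on assumptions.** This stands. The 88% needs flat controls and modest slope variance. The 11% counts both directions, and most of those results would not be read as durability. The simulated figure for that setting (17%) is also higher than the analytic one.
- **Reporting L × g would do.** It would with flat controls (fitted +0.009 when the truth is 0) and when the effect persists. It fails when the effect is gone and controls drift, as in step 3.
- **A loss would be visible in the week-48 scores.** Probably so, but without a test or interval beside a significant coefficient.

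**Conclusion.** The concern holds. A significant group coefficient does not establish a CDR-SB difference at week 48, and no other planned test does. That conclusion is algebraic and firm.

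The size is illustrative. For a 0.3 SD benefit wholly lost by week 48, the planned test is significant in 11% to 88% of trials across the control trends examined. When controls are stable it hardly separates loss from persistence. When they worsen by 0.20 SD or more by week 24, the coefficient turns the wrong way. These figures depend on the assumed correlations, slope variance and drift, none of which the documents give. The point should be fixed, but it concerns one secondary-aim outcome and leaves the 24-week primary analyses untouched.

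**What to change.** Define the CDR-SB durability test as the between-arm difference in change from baseline to week 48, for each of the two comparisons with the enhanced arm. Take it from the Group by Time mixed model, extended to four visits with categorical time and an unstructured visit covariance. The unstructured covariance departs from the random-intercept model now written, so the SAP should say so. It should also say whether these two contrasts depend on a significant Group by Time interaction. Keep the growth curve as description and report L beside g.

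If a growth model must carry the inference, code time in weeks with an on-treatment slope (0, 16, 24, 24) and a post-treatment slope (0, 0, 0, 24). Fix the variance of the latter, for example at zero, because only one visit informs it. Regress both slopes on arm and test the total week-48 effect. Under the assumptions above this rejects in about 5% of trials if the benefit is gone and 75–77% if it persists.

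The cost is SAP wording and one model contrast, with no new data. The direct contrast has 67% power for a kept 0.3 SD benefit, against 88% for g with flat controls, but that 88% is not power for a week-48 difference. The documents are dated September 2024 and describe the modifications in the past tense. If 48-week data have already been analysed, report the new contrast as post hoc beside the planned coefficient.

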Mild cognitive impairment (MCI) is an intermediate stage between the common phenomenon of cognitive decline with aging and the more pronounced decline of dementia due to Alzheimer's disease (AD).^{1,2} Approximately 16%-20% of adults over age 65 have MCI,³ exposing these individuals to a higher risk of developing AD. Estimates show that more than 30% of individuals with MCI progress to developing dementia related to AD within 5 years.^{4,5} These data call for an increased effort and demand to develop and test effective cognitive health care strategies that can prevent cognitive decline and slow the progression of MCI to AD.

Exercise plays an important protective role in preserving cognitive function or mitigating the progression of cognitive impairment for older adults with MCI. 6-8 Among various exercise modalities, tai ji quan represents one of the promising mind-body integrative therapeutics for promoting brain health. 9 However, studies examining the clinical impact of tai ji quan on influencing MCI remain insufficient to inform evidence-based recommendations due to (a) the limited number of rigorously designed studies and (b) the lack of explicit integration of a cognitive training component that could further boost its cognitive benefit. As a result, it is difficult to synthesize research findings and confirm the clinical merit or public health impact of tai ji quan in promoting and preserving cognitive function in people with cognitive impairment, including MCI.

Study Aims

Primary Aim. The primary aim of this study is to determine the effectiveness of a cognitively enhanced tai ji quan exercise intervention, compared to a standard tai ji quan intervention and an exercise stretching control, in improving cognitive function and dual-task walking ability among community-dwelling older adults with MCI. On the basis of preliminary results, ¹⁰⁻¹² the primary hypothesis is that during a 6-month intervention, participants receiving enhanced tai ji quan training, compared to participants receiving either a standard tai ji quan intervention or stretching exercise control, will show greater improvement in the primary outcome measures of global cognitive function and dual-task walking ability. Secondary outcomes include cognitive impairment and domain-specific cognitive function and physical performance measures.

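### The sign of one arm's CDR-SB slope cannot show that disease progression was lowered; statements about progression should rest on the between-arm slope coefficient already planned

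*Protocol*

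**What the plan says.** The SAP section on intervention durability at 48-week follow-up (the same text stands in the Protocol's SAP chapter) fits a latent growth curve to CDR-SB at baseline and weeks 16, 24 and 48. It will report a slope mean for each arm and a coefficient for the regression of slope on group; the 95% confidence interval is attached to the coefficient. It then gives a reading rule for the arm slopes: "A negative slope mean for CDR-SB will indicate an improvement in cognitive functioning and, therefore, a lowering of the disease progression". A slope mean above zero is to be read as worsening.

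The secondary hypothesis (Study aims, both documents) speaks of "sustaining the training effect on slowing disease progression to dementia" and takes as its index whether the mean CDR-SB score keeps improving on its baseline value.

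The same durability section also plans a comparison. Slope is regressed on group for the enhanced arm "compared with each of other two active groups, individually, on the rate of change in cognitive functioning trajectories", and "A statistically significant regression coefficient indicates the difference in the rate of CDR-SB progression". Tests are two-sided and "statistical significance will be defined as a P value of <0.05".

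**The concern.** Lowering of progression is a contrast between what happened and what would have happened without the intervention. The slope mean of a single arm contains no such contrast. All three arms receive a 48-session exercise programme. The Protocol describes stretching as matched to the tai ji quan arms on social contact and other accompaniments of taking part, and the durability section calls both comparators active. The only natural-course figure in the documents is that "more than 30% of individuals with MCI progress to developing dementia related to AD within 5 years" (Protocol, Study Background and Rationale). That is a conversion proportion and not a CDR-SB rate.

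At stake is what the trial may say about its secondary aim. Followed as written, the rule lets the report state that progression was lowered in any arm with a negative slope, whatever the comparison between arms shows.

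**Working it through.** The documents give no CDR-SB rate, SD, effect size or power, so there is no figure of the plan's to reproduce. All values of g, e, SD and the means below are assumptions, in CDR-SB points.

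**1. What the sign measures.** Write an arm's slope as s = g + e, where g is the course without the intervention and e is the intervention's effect. Lowering of progression means e < 0. The rule reads the sign of g + e.

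| g | e | g + e | Reading under the plan | What the intervention did |
|---|---|---|---|---|
| −0.1 | 0 | −0.1 | progression lowered | nothing |
| −0.3 | +0.2 | −0.1 | progression lowered | harm |
| +0.1 | −0.4 | −0.3 | progression lowered | lowered it (rule is right) |
| +0.5 | −0.4 | +0.1 | deterioration | prevented 0.4/0.5 = 80% of the decline |

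A negative g could come from regression to the mean, repeat rating or expectation. CDR is a repeated interview with participant and informant (Protocol, Clinical Dementia Rating), and participants are not masked. The documents do not quantify any of these.

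**2. The index in the hypothesis.** In the last row, a positive slope is correctly described as deterioration. Yet that arm fails an index based on continuing improvement from baseline, even though it declined less than an arm with slope +0.5.

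**3. Sampling error.** No confidence interval is specified for the arm slopes, so the rule would act on a point estimate.

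- If true change is zero in all arms, each estimate is negative with probability 0.50, and at least one of three with probability 1 − 0.5³ = 0.875.
- With 315/3 = 105 per arm, a true worsening of 0.1 and no effect, P(negative estimate) = Φ(−0.1/(SD/√105)). This treats the slope as a simple mean change. It gives 0.09 for an SD of 0.75, 0.15 for 1.0 and 0.25 for 1.5.

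**4. The free week-48 loading.** The slope loadings are 0, 1 and 2 at baseline and weeks 16 and 24; the week-48 loading is estimated. The model-implied mean is intercept + loading × slope. Take assumed means of 1.5, 1.35, 1.2 and 1.7:

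- slope = 1.35 − 1.5 = −0.15, which also fits week 24: 1.5 + 2 × (−0.15) = 1.2;
- week-48 loading = (1.7 − 1.5)/(−0.15) = −1.33.

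A maximum-likelihood fit under two assumed covariance structures gave −1.33 and −1.36. The slope is negative, so the rule says progression was lowered, although the week-48 mean is 0.2 worse than baseline.

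**5. The between-arm coefficient.** With a common untreated course, which randomization provides in expectation, (g + e₁) − (g + e₂) = e₁ − e₂ for any g. The contrast removes what the sign rule cannot. For slopes of +0.1 (enhanced) and +0.5 (stretching) the difference is −0.4, in favour of enhanced. For −0.3 and −0.5 it is +0.2, in favour of stretching, while the sign rule would call both arms lowered.

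**The case against.** The strongest reply is that the plan already tests the right thing. The durability section states its hypothesis as a rate of improvement greater than in the other two arms, estimates that contrast, and gives it a confidence interval and a two-sided test. The secondary hypothesis also speaks of superiority to each comparator. This stands. A reader might infer that the secondary objective is answered by a sign alone, or that the CDR-SB test is invalid; the documents support neither. The coefficient does not use the sign rule and settles both examples in step 5.

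A reader might also infer that the rule is equally wrong for positive slopes. It is not. Calling a positive slope deterioration is accurate on a scale where higher is worse, and the plan draws no conclusion about progression from it. The difficulty on that side lies only in the hypothesis's index.

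Third, if untreated MCI worsens, as the Protocol's background suggests, a truly negative slope would be a lowering. That is fair, but the documents cannot show that the enrolled sample would have worsened on CDR-SB over 48 weeks. Entry allows a global CDR of 0. Regression to the mean could run either way, since entry requires a memory complaint but also caps the CDR.

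Finally, a reader might fault the trial for too few conversions to dementia in 48 weeks. No conversion endpoint or test is planned, so a power figure for one would not measure this fault.

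**Conclusion.** The interpretation rule is wrong as written; severity is low to moderate. A stated inference in both documents, echoed by the index in the secondary hypothesis, permits a conclusion about disease progression that no single arm can support. No estimate, test or sample size is affected, and the randomized between-arm coefficient remains valid.

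The logical point rests only on what the documents show: no untreated arm, no external CDR-SB rate, and a free week-48 loading. How often the rule would mislead depends on quantities that the documents do not give, so the probabilities above are illustrations. Even the coefficient supports only a statement relative to standard tai ji quan or to stretching, not relative to no intervention.

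**What to change.** - In the durability section of both documents, keep the statement that a negative slope is an improvement in functioning and strike the inference to disease progression that follows it.
- Present arm slopes as descriptive only, each with a confidence interval and with the estimated week-48 loading or the model-implied change to week 48.
- Base every statement about progression on the planned between-arm slope coefficient with its 95% confidence interval, worded as relative to standard tai ji quan or relative to stretching.
- In the secondary hypothesis of both documents, replace the slowing of progression to dementia, and its index of improvement from baseline, with a more favourable rate of change in CDR-SB than in each comparator. Keep it a rate: a level at week 48 would not match what the slope coefficient tests.

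The cost is wording plus a few quantities that the fitted model already yields. No new data are needed. The price is a more modest secondary claim.
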